### 6.3 ANALYSIS OF GLUCOSE MEASURES

Mean glucose, glucose measurement indicator (GMI), standard deviation (SD) of glucose and coefficient of variation (CV) of glucose will be evaluated per subject based on CGM output. The GMI and CV are calculated as follows:

$$GMI (\%) = 3.31 + 0.02392 \times (\text{mean glucose in mg/dL})$$

## Statistical Analysis Plan

$$CV(\%) = \frac{SD \text{ of glucose}}{\text{mean glucose}}$$

### 6.4 ANALYSIS OF INSULIN REQUIREMENTS

Insulin requirements (TDI, total daily basal insulin and total daily bolus insulin) during the hybrid closed-loop phase will be compared to the standard therapy phase. The insulin requirements will be collected at Visit 2 (start of ST phase) and compared to the data collected by the Horizon™ System during HCL:

- Total daily insulin: sum of basal and bolus insulin reported over the course of HCL, adjusted for 24-hour period
- Total daily basal insulin: sum of basal insulin reported over the course of HCL, adjusted for 24-hour period
- Total daily bolus insulin: sum of bolus insulin reported over the course of HCL, adjusted for 24-hour period. This will include only bolus insulin administered and recorded by the Horizon™ System.

Data will be summarized both in insulin units and units/kg to provide a weight-adjusted comparison.

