#### **8.1 Visit 2**

**Visit 2** represents the commencement of the standard therapy phase. All scheduled assessments will be performed according to Table 2: Schedule of Assessments. This visit will include:

- Review of concomitant medications
- Average total daily insulin (approximately over the past 7 days)
- Average total daily basal insulin (approximately over the past 7 days)
- Average total daily bolus insulin (approximately over the past 7 days)
- Review pump settings/MDI dosing
- Completion of questionnaires (see Table 3: Questionnaires for specific requirements by age group):
  - WHO-5
    - Used to measure current mental well-being
  - EQ-5D
    - Used to measure quality of life
  - T1DDS
    - Used to measure four critical dimensions of distress
  - DTSQs
    - Used to measure satisfaction with diabetes treatment regimens
  - Hypoglycemia Confidence Scale
    - Used to measure hypoglycemia unawareness, hypoglycemia frequency, severity and impact
  - HABS
    - Used to measure critical dimensions of hypoglycemia related concerns and confidence
  - PSQI
    - Used to measure sleep disturbance and usual sleep habits
  - IDSS (T1)
    - Used to measure patient satisfaction with their devices and impact on quality of life
  - SUS

- Used to measure usability of a system
- PAID-(Teen, Child)
  - Measures diabetes-related burden
- Training on Glucagon administration and information on treatment of hypo/hyperglycemia
  - All subjects are required to have access to glucagon and receive training on how to deliver the medication
- Study device training per manufacturer's instructions (CGM - blinded, BG, and ketone meters)
- Dispensing of CGM (blinded for non-G6 users), BG, and ketone meter
- QC testing of BG and ketone meter
  - Must pass at least one level of quality control testing prior to dispensing
- CGM sensor placement (if applicable)
  - Approved anatomical locations for CGM sensor placement will be reinforced as well as the importance of using approved locations

During this visit, subjects will be dispensed the following supplies:

- Dexcom transmitter
- Dexcom receiver
- Dexcom sensors
- Contour® Next One blood glucose meter
- Contour® Next One blood glucose meter test strips
- Contour® Next One blood glucose meter control solution
- Lancets
- Precision Xtra blood ketone meter
- Precision Xtra blood ketone meter test strips
- Precision Xtra blood ketone meter control solution

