Subjects will be provided, by the site, information regarding treatment of hypoglycemia and hyperglycemia including sick day management and emergency management of severe hypoglycemia and diabetic ketoacidosis. Subjects will be given contact information for study personnel and product support.

If a subject is on MDI, the investigator will advise the subject on the treatment regimen to reduce insulin depending on the insulin action profile of injected doses prior to the commencement of the hybrid closed-loop phase. MDI subjects will be required to keep a log to record daily doses of insulin during the standard therapy phase.

## 8.2 Visit 3

**Visit 3** will be conducted in person at the clinical study site one (1) day prior to the start of the hybrid closed-loop phase. All scheduled assessments will be performed according to Table 2: Schedule of Assessments. This visit will include assessment of whether subjects have met the CGM usage and data criteria.

Prior to the commencement of the hybrid closed-loop phase, subjects must meet the following criteria:

- At least 80% CGM use (11.2-days) during any consecutive 14-days in the past 30-days and
- $\geq 2,016$  CGM values during the 14-days

If the CGM criteria is not met, the standard therapy phase may be extended, per investigator discretion, or the subject may be withdrawn from the study. At the conclusion of the standard therapy phase, if the investigator determines that there have been no safety concerns, the subject will continue to the hybrid closed-loop phase. If the investigator determines that it is unsafe for the subject to continue into the hybrid closed-loop phase, the subject will not be allowed to continue in the second phase of the study, and the reason for study exit will be documented.

## 9 HYBRID CLOSED-LOOP - PHASE 2

The hybrid closed-loop phase will commence at **Visit 4** upon the conclusion of the standard therapy phase and after all assessments are performed according to Table 2: Schedule of Assessments.

During the hybrid closed-loop phase, subjects will be asked to do the following:

- Adjust pump and CGM parameters to optimize their insulin therapy in collaboration with the recommendations from the clinical study staff
- Follow their pre-exercise management such as insulin reduction for meal boluses, consumption of snacks, or adjusting their insulin delivery settings

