- Treat themselves per their usual routine if they become hypoglycemic or hyperglycemic or have symptoms of either at any time during the study
- Consume meals and snacks of their own choosing. Subjects will be encouraged to estimate the grams of carbohydrates for each meal or snack per their usual routine. The estimate should be entered into the meal bolus calculator.
- Administer meal boluses per their usual dosing routine
- Participate in target BG challenges as specified
- Change their CGM per manufacturer's instructions or sooner if necessary
- Change the Pod at least once every 72 hours
- Complete questionnaires (Table 3: Questionnaires)

Subjects will have scheduled follow-up visits according to Table 2: Schedule of Assessments and complete questionnaires according to Table 3: Questionnaires. Visits will be conducted either in the hotel/rental house environment, in person at the clinical study site or over the telephone. Subjects may also choose to use email or text as a substitute for their scheduled telephone visit.

The duration of the hybrid closed-loop phase will last 14-days.

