## 11.2 Hypoglycemia/Hyperglycemia

Subjects will be asked to treat per their usual routine if they suspect either hypoglycemia or hyperglycemia, either by confirmation of hypoglycemia with a fingerstick BG, symptoms, or perceived risk.

Subjects will be encouraged to manage their hyperglycemia per their usual routine. This includes checking for ketones using the study-approved ketone meter and administering a correction bolus if needed.

In the event of unexplained hyperglycemia, where the CGM is  $>300\text{mg/dL}$  for 1h or  $>250\text{ mg/dL}$  for 2h, blood glucose (measured with BG meter) and ketones should be checked. If BG is  $\geq300\text{ mg/dL}$  and ketones are  $>1.0\text{ mmol/L}$ , an occlusion or dislodged cannula should be suspected. The Pod should be removed, and the subject will be instructed to replace the Pod. Subjects should contact the clinical site for further instructions to determine whether an additional injection of insulin is required. This prolonged hyperglycemic event, defined as meter BG  $\geq300\text{ mg/dL}$  and ketones  $>1.0\text{ mmol/L}$ , will be recorded as an adverse event and cause may be attributed to suspected occlusion if the cannula is in situ or dislodged cannula if it has been pulled out. Pods will be requested to be returned to Insulet for analysis. An Adverse Event form will be completed per the Reportable Adverse Events section below.

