## 13.2 Electronic Device Outputs

### 13.2.1 PDM Data

This study will utilize insulin delivery data from the PDM device. All insulin delivery data and all CGM readings from the hybrid closed-loop phase will be stored on the PDM and exported to Insulet Cloud. Data will be saved in a compatible format that will be extractable for statistical analysis purposes. Data from the hybrid closed-loop phase will be uploaded to the database and used for analysis.

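### Closed-loop insulin is limited to what the Horizon System recorded, while the standard therapy value has no matching limit and no defined source

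*SAP*

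**What the plan says.** **Closed-loop side.** SAP 6.4 draws closed-loop insulin from data collected by the Horizon System. Total insulin is defined as: "Total daily insulin: sum of basal and bolus insulin reported over the course of HCL, adjusted for 24-hour period". For bolus insulin it adds: "This will include only bolus insulin administered and recorded by the Horizon™ System". Protocol 13.2.1 names the same source: "This study will utilize insulin delivery data from the PDM device".

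**Standard therapy side.** SAP 6.4 takes the comparator from Visit 2, at the start of the standard therapy phase. Protocol 8.1 describes it as average total, basal and bolus daily insulin over roughly the preceding 7 days. Neither document says whether it comes from a pump download, a log or recall, and neither restricts it to insulin delivered by a device.

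**Insulin outside the system in closed-loop.** Protocol 11.2, on unexplained hyperglycemia with a suspected occlusion or dislodged cannula, says: "Subjects should contact the clinical site for further instructions to determine whether an additional injection of insulin is required".

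**Recording.** Closed-loop visits review concomitant medications (protocol 9.3 to 9.7), documented only when something has changed (Table 2, footnote e). No section asks for the dose of insulin injected during closed-loop, and SAP 6.4 has no rule for adding it.

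**The concern.** The endpoint is called insulin requirements. If a Pod fails to deliver and the subject injects insulin, that insulin was needed, but the SAP leaves it out of the closed-loop total. The omission works in one direction: it can lower the closed-loop figure and never raise it. By the route in protocol 11.2 it falls on subjects with delivery problems, so it is not random noise.

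The contrast is clearest for MDI users. Their Visit 2 value consists of injected insulin, whereas an injection in closed-loop is excluded by rule. Protocol section 7 advises sites to recruit at least 20% of subjects using MDI, about 7 of 36 (0.20 × 36 = 7.2).

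At stake is a small bias toward a lower apparent insulin need on the device. It concerns what is counted and is separate from the timing of the Visit 2 value: it would remain if that value covered the standard therapy phase itself.

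**Working it through.** The plan states no expected dose, number of injections, standard deviation or power for this endpoint, so there is no figure to reproduce. The check has two parts.

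**1. What each side counts**

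| | Standard therapy value | Closed-loop value |
|---|---|---|
| When | About 7 days before Visit 2 | 14-day closed-loop phase |
| Source | Not stated | Horizon System (PDM) data |
| Bolus limit | None stated | Horizon-administered and recorded only |
| Basal limit | None stated | None in words; limited through the data source |
| Total | Average total daily insulin | Basal plus bolus, so the bolus limit carries over |
| Injected insulin, MDI users | It is the value | Left out |
| Injected insulin, pump users | Depends on the undefined source | Left out |

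**2. Scale, on assumed figures**

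From the documents: 14 closed-loop days. Assumed: total daily insulin of 20 to 60 units, 1 to 3 unrecorded injections, 2 to 10 units each.

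Share of total insulin omitted for an affected subject = (units per injection × number of injections) / (14 × total daily insulin).

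- Reference case, one 10-unit injection at 40 units/day: 10 / (14 × 40) = 10/560 = 1.8%.
- Low end, one 2-unit injection at 60 units/day: 2 / (14 × 60) = 2/840 = 0.2%.
- High end, three 10-unit injections at 20 units/day: 30 / (14 × 20) = 30/280 = 10.7%.
- Bolus insulin in the reference case, assuming a 50% bolus share: 10 / (14 × 20) = 10/280 = 3.6%.

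The endpoint is summarized by age cohort, so the per-subject share must be multiplied by the share of subjects affected. Assume 20% are affected and all have the same total daily insulin:

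- Reference case: 0.20 × 1.8% = 0.36%, about 0.4% of the cohort mean.
- Low and high ends: 0.20 × 0.2% = 0.04% and 0.20 × 10.7% = 2.1%.

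These results show scale only. They are not estimates of what the study would find.

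**The case against.** The strongest reply is that the restriction is stated openly, so a reader of the SAP knows what is counted. The endpoint is secondary, has no hypothesis and will not support clinical claims (SAP 6.5). SAP 7.2 relies on direct device output for objectivity, and a total that includes self-reported doses gives up some of that. The episodes are also largely traceable: meter glucose of at least 300 mg/dL with ketones above 1.0 mmol/L is a reportable event, and so is contacting the site and receiving guidance on hyperglycemia or ketosis (protocol 11.3.4). Most of this stands. It keeps the point minor and argues against making a self-reported total the main figure. It does not supply a dose field or a summation rule, and doses not recorded at the time cannot be reliably recovered later.

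A reader might also infer more than the documents support:

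- **That the standard therapy value counts all insulin by every route.** No section says so. If a pump user's value came from a pump download, injections could be missing there too.
- **That former MDI users would treat high glucose with a pen.** Protocol section 9 has subjects "Treat themselves per their usual routine if they become hypoglycemic or hyperglycemic", but no section mentions a pen, and protocol 11.2 describes ketone checks and a correction bolus. The documented route is the conditional injection in 11.2.
- **That a dose log protects one side only.** Protocol 8.1 says: "MDI subjects will be required to keep a log to record daily doses of insulin during the standard therapy phase". That log starts after the Visit 2 average is taken, and SAP 6.4 does not use it.
- **That a full day off the Pod would cost 1/14 = 7.1%.** Protocol 11.2 calls for Pod replacement, not a day on injections, and the figure depends on the denominator of the 24-hour adjustment, which SAP 6.4 does not define.

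**Conclusion.** The point holds in a limited form. By a stated rule, closed-loop bolus insulin, and through it total daily insulin, excludes insulin injected outside the Horizon System, although the protocol foresees that such an injection may be required. The comparator has no matching rule. The asymmetry is clear for MDI users; for pump users it cannot be settled until the source of the Visit 2 value is stated.

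The direction is certain: any such injection understates closed-loop insulin. The size is unknown and probably small at cohort level, about 0.4% in the reference case. That rests on an assumed 10-unit injection, 40 units/day and 20% of subjects affected. For a single affected subject the assumed range is 0.2% to 10.7%. The primary and safety endpoints are not touched. The change is worth making because it is cheap, but the study does not depend on it.

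**What to change.** 1. During closed-loop, record the dose and type of any insulin injected outside the system, using the site contacts, adverse event reports and concomitant-medication reviews that already exist.
2. In SAP 6.4, report total daily and bolus insulin in two forms: Horizon-recorded only, and with recorded injections added. Any long-acting insulin goes to basal, with basal shown both ways if so. The Horizon-only figure can stay the main one.
3. State the source of the Visit 2 value separately for pump and MDI users, and whether it includes injections given by pump users.
4. While editing SAP 6.4, define the denominator of the 24-hour adjustment, so that the two forms are computed over the same time.

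The cost is a few lines in the SAP, a dose field on existing forms and one extra set of summary rows. The downside is that injected doses are self-reported, and showing both figures makes that visible. No change to when or how insulin is given is proposed.

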### 6.5 ANALYSIS OF SECONDARY EFFECTIVENESS ENDPOINTS

There are no pre-specified hypotheses associated with the secondary effectiveness endpoints. Summary statistics will be presented by age cohort for all endpoints, stratified by time points of interest (e.g., day, night, overall). All statistical comparisons will be conducted at a two-sided significance level of 5%. If the assumptions for parametric tests are grossly violated, a non-parametric method such as Wilcoxon signed rank test may be used. Since the results of endpoint analyses will not be used to support clinical claims, no adjustment for multiplicity will be performed.

As described in this document, results will be stratified by phase of the study (ST versus HCL), age group (subjects aged 6-13.9 years versus subjects aged 14-70 years) and day versus night (daytime: 6AM to <12AM; nighttime as 12AM to <6AM). Results for other subgroups may be presented as appropriate.

## 7 GENERAL STATISTICAL CONSIDERATIONS

### 7.1 ANALYSIS SETS

The following analysis sets are planned for the study.

## Statistical Analysis Plan

---

### 7.1.1 ITT (Intention to Treat) Analysis Set

The ITT analysis set includes all subjects that are enrolled in the study. All safety analyses (other than primary analysis for primary safety endpoints) will be based on the ITT analysis set.

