#### 6.1.2 Secondary Safety Endpoints

- Proportion of subjects with severe hypoglycemia during hybrid closed-loop
- Proportion of subjects with diabetic ketoacidosis (DKA) during hybrid closed-loop

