### 12.3.1 ITT (Intention to Treat) Analysis Set

The ITT analysis set includes all subjects that are enrolled in the study. All safety analyses (other than primary analysis of primary safety endpoints) will be based on the ITT analysis set.

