### 12.3.2 mITT (modified Intention to Treat) Analysis Set

The modified Intention to Treat (mITT) analysis set is a subset of the ITT analysis set. The mITT analysis set will consist of subjects who have entered the hybrid closed-loop phase of the study successfully. The mITT analysis set will be used as the primary analysis for the primary and secondary endpoints and other clinical outcome data.

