### **1 PURPOSE**

The purposes of this Statistical Analysis Plan (SAP) is to describe the statistical methodology that will be used to confirm the safety and effectiveness of the Omnipod Horizon™ Automated Glucose Control System in patients with type 1 diabetes. Should there be any discrepancy between the study protocol and this SAP, the content of the SAP shall prevail.

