## **3 STUDY OBJECTIVES AND ENDPOINTS**

### **3.1 SAFETY OBJECTIVES AND ENDPOINTS**

The primary safety objective is to evaluate the safety of the Omnipod Horizon™ Automated Glucose Control System in patients with type 1 diabetes. The safety objective will be evaluated by summarizing the following endpoints during HCL:

- Primary safety endpoint:
  - Proportion of subjects with serious device-related adverse events
- Secondary safety endpoints:
  - Proportion of subjects with severe hypoglycemia
  - Proportion of subjects with diabetic ketoacidosis (DKA)

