### 5.4 ANALYSIS OF ADVERSE EVENTS

Safety summaries and analyses will be based on all subjects that are enrolled in the study (i.e., Intention to Treat analysis set). All adverse events reported over the course of the study will be summarized and tabulated by study phase (standard therapy or HCL), event category, seriousness, severity, and relationship to the study procedures and the investigational device. Except where indicated, a subject reporting the same adverse event more than once will be counted once when calculating the number and percentage of subjects with that particular event. Adverse Event outcomes will be assessed descriptively as opposed to inferentially.

Adverse events leading to death or to discontinuation from the study will be listed separately. A listing of all adverse events will be provided. No formal tests of hypotheses are proposed for the safety endpoints.

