### 7.1.2 mITT (modified Intention to Treat) Analysis Set

The mITT analysis set is a subset of the ITT analysis set. The mITT analysis set will consist of subjects who have entered the hybrid closed-loop phase of the study successfully. The mITT analysis set will be used as the primary analysis set for all primary and secondary endpoints (both safety and effectiveness), and other clinical outcome data.

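### The SAP assigns severe hypoglycemia and DKA during hybrid closed-loop to ITT in 7.1.1 and to mITT in 7.1.2, so their denominator is defined twice

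*SAP*

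**What the plan says.** Three sections of the SAP assign an analysis set to safety results.

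- SAP 7.1.1: "All safety analyses (other than primary analysis for primary safety endpoints) will be based on the ITT analysis set". ITT is everyone enrolled.
- SAP 7.1.2: "The mITT analysis set will be used as the primary analysis set for all primary and secondary endpoints (both safety and effectiveness". mITT is the part of ITT that entered the HCL phase.
- SAP 5.4: "Safety summaries and analyses will be based on all subjects that are enrolled in the study (i.e., Intention to Treat analysis set". No exception is stated.

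The protocol has the same pair of rules. Section 12.3.1 reads "All safety analyses (other than primary analysis of primary safety endpoints) will be based on the ITT analysis set" and section 12.3.2 reads "The mITT analysis set will be used as the primary analysis for the primary and secondary endpoints and other clinical outcome data". The second of these does not mention safety by name.

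SAP 3.1 lists one primary safety endpoint (serious device-related adverse events) and two secondary ones (severe hypoglycemia and DKA), under the lead-in "The safety objective will be evaluated by summarizing the following endpoints during HCL". Protocol 6.1.2 limits the secondary endpoints to the same phase, for example "Proportion of subjects with severe hypoglycemia during hybrid closed-loop".

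**The concern.** For the two secondary safety endpoints, 7.1.1 and 7.1.2 cannot both be followed. Two analysts working from the same SAP could report different percentages for the same endpoint, each with a section to cite.

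Any difference goes one way. A subject is enrolled at placement of the first study CGM (SAP 2.7), which for non-G6 users comes at the start of standard therapy. The documents foresee exits before HCL: lost eligibility (Protocol 7.1, Enrollment), unmet CGM criteria or a safety concern (Protocol 8.2), and subjects who never reach the phase (SAP 7.6). Such a subject cannot have an event during HCL. ITT therefore adds only non-events and lowers the reported proportion.

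What is at stake is a clean descriptive estimate for two of the three named safety endpoints, with the denominator settled before data are seen.

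**Working it through.** **Step 1: the sections side by side**

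| Endpoint (SAP 3.1, during HCL) | SAP 7.1.1 | SAP 7.1.2 | SAP 5.4 |
|---|---|---|---|
| Primary: serious device-related adverse events | Excepted from ITT | mITT | ITT |
| Secondary: severe hypoglycemia | ITT | mITT | ITT |
| Secondary: DKA | ITT | mITT | ITT |

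Sections 7.1.1 and 7.1.2 agree on the primary endpoint and disagree on both secondary ones. Section 5.4, read literally, disagrees with 7.1.2 on all three.

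**Step 2: does the precedence clause settle it?** SAP 1 says "Should there be any discrepancy between the study protocol and this SAP, the content of the SAP shall prevail". That ranks the SAP above the protocol. It gives no rule for two SAP sections that disagree.

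**Step 3: size.** The plan states no denominator and no rate of loss before HCL, so there is no planned figure to reproduce. The inputs are:

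- Up to 48 enrolled to obtain at least 36 evaluable (SAP 4.1).
- Group 1 has 16 subjects and Group 2 has 20 (SAP 2.3); 16 + 20 = 36.
- Assumption: 36 subjects enter HCL. The documents do not define evaluable as mITT.
- Assumption: all loss before HCL falls in Group 2. Exempt G6 users may start HCL at once (Protocol 8), and Group 1 is expected to consist of G6 users (Protocol 5.2).

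Let k be the number enrolled who leave before HCL, so ITT N = 36 + k. Relative dilution is 1 − 36/N. One affected subject reads 1/N on ITT and 1/36 = 2.78% on mITT. The share of Group 2 lost is k/(20 + k).

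| k | N | Relative dilution | 1/N | Difference from 2.78% (points) | Group 2 lost |
|---|---|---|---|---|---|
| 0 | 36 | 0% | 2.78% | 0 | 0% |
| 1 | 37 | 2.7% | 2.70% | 0.08 | 4.8% |
| 2 | 38 | 5.3% | 2.63% | 0.15 | 9.1% |
| 5 | 41 | 12.2% | 2.44% | 0.34 | 20.0% |
| 12 | 48 | 25.0% | 2.08% | 0.69 | 37.5% |

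The last row is the enrollment cap. It needs 12 of 32 Group 2 subjects to leave before HCL, which is unlikely.

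**Step 4: how often would a non-zero count arise?** This is a rough guide only. It takes the highest rates in Protocol Table 6 (7% severe hypoglycemia, 4% DKA). The table gives no period, so 3 to 12 months (91.25 to 365 days) is assumed. Expected affected subjects = 36 × rate × 14/period.

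- Severe hypoglycemia: 36 × 0.07 × 14/365 = 0.10, up to 36 × 0.07 × 14/91.25 = 0.39. The Poisson chance of no affected subject is 0.91 down to 0.68.
- DKA: 36 × 0.04 × 14/365 = 0.06, up to 36 × 0.04 × 14/91.25 = 0.22. The chance of none is 0.95 down to 0.80.

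On these assumptions zero is the likeliest count for each endpoint, and both sets then report 0%.

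**The case against.** The best defense is that a workable reading exists. Section 7.1.2 is the only place that expressly assigns secondary safety endpoints to a set. Section 7.1.1 reaches them only through a loosely drafted parenthesis, which uses the plural although SAP 3.1 lists a single primary safety endpoint. If the specific rule governs the general one, mITT is primary, ITT covers the remaining safety tables, and an extra ITT presentation is not ruled out. Section 5.4 sits under an adverse event heading and goes on to describe tables by phase, for which ITT is appropriate.

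That reading is sensible and probably what was intended, but the text does not deliver it. The writer of 7.1.1 gave an exception and limited it to primary endpoints; had mITT been meant for the secondary ones, they would belong in that exception. The opening sentence of 5.4 covers safety analyses in general, and the section later speaks of the safety endpoints. Even without 5.4, sections 7.1.1 and 7.1.2 conflict.

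Two criticisms of the numbers stand:

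- Group 2 is expected to include some G6 users. If only non-G6 users are at risk of leaving before HCL, the loss needed among them exceeds the Group 2 percentages shown, and the larger scenarios become less plausible.
- The Table 6 estimate applies an adult rate to a sample half of which is aged 6-13.9. It uses a narrower definition of severe hypoglycemia than Protocol 11.3.3, and it ignores the exclusion of subjects with recent events. These push in different directions, so it is not a bound. The conclusion does not depend on it.

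It also stands that the numerator is the same under both sets, that no safety hypothesis is tested and every adverse event is listed (SAP 5.4), that there is no success criterion (SAP 2.5), and that percentages come with frequencies (Protocol 12.8).

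**Conclusion.** The concern holds, at minor severity and with high confidence in the textual conflict. The SAP gives two denominators for severe hypoglycemia and DKA during HCL, a third statement in 5.4 unsettles the primary safety endpoint too, and nothing in the documents decides between them. ITT is also the poorer choice for endpoints confined to HCL, because it can only dilute them.

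The effect is limited to descriptive percentages. For one affected subject the difference is 0.08 to 0.34 percentage points if 1 to 5 subjects leave before HCL, and 0.69 at the enrollment cap. These figures rest on the assumption that 36 subjects enter HCL. The difference is zero if all enrolled subjects enter HCL or if no events occur.

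**What to change.** In SAP 5.4, SAP 7.1.1 and Protocol 12.3.1, state that the primary and secondary HCL safety endpoints are analyzed on mITT. In 7.1.1 and 12.3.1 this means widening the existing exception to cover the secondary safety endpoints; in 5.4 it means adding the exception. Keep ITT for the adverse event tabulations across both phases and for the listing of all adverse events. SAP 7.1.2 and Protocol 12.3.2 can stay as they are.

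The cost is wording in three sections, with no new data and no new analysis. The reported HCL proportions may be slightly higher than they would be on ITT.
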